#### **4.3. Safety Analysis Population**

The safety analysis (SAF) population will include all subjects who receive at least 1 dose of an investigational product. For reactogenicity analyses by dose/lot, subjects who received a different dose/lot from the dose/lot they were assigned will be included in the SAF population for the summaries of individual vaccinations up until the point their dose/lot differs from the assigned dose/lot, at which point they will no longer be included. For AE analysis, such subjects will be included in the AE summary in the group according to the first vaccine dose/lot received.

[figure not shown]

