8.4.4.1. Medication Errors

Medication errors may result from the administration or consumption of the investigational product by the wrong subject, or at the wrong time, or at the wrong dosage strength.

Medication errors include:

- Medication errors involving subject exposure to the investigational product;
- Potential medication errors or uses outside of what is foreseen in the protocol that do or do not involve the participating subject.

Other examples include, but are not limited to:

- The administration of expired investigational product;
- The administration of an incorrect investigational product;
- The administration of an incorrect dosage;
- The administration of investigational product that has undergone temperature excursion from the specified storage range, unless it is determined by the sponsor that the investigational product under question is acceptable for use.

Such medication errors occurring to a study participant are to be captured on the medication error page of the CRF, which is a specific version of the AE page.

In the event of a medication dosing error, the sponsor should be notified immediately.

Whether or not the medication error is accompanied by an AE, as determined by the investigator, the medication error is recorded on the medication error page of the CRF and, if applicable, any associated AE(s), serious and nonserious, are recorded on an AE page of the CRF.

Medication errors should be reported to Pfizer Safety within 24 hours on a CT SAE Report Form **only when associated with an SAE**.

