9.2. Immunogenicity Analysis

The immunogenicity data will be summarized according to the vaccine group (active vaccine and placebo) as received in the evaluable immunogenicity population, and according to the vaccine group as randomized in the modified intent-to-treat (mITT) population. Subjects receiving vaccine who did not follow their randomization assignment will be excluded from the evaluable immunogenicity population.

The *C difficile* toxin A– and toxin B–specific neutralizing antibody levels at each blood sampling time point will be summarized by GMCs (any *C difficile* toxin A– or toxin B–specific neutralizing antibody level that is below the lower limit of quantitation [LLOQ] will be assigned as $0.5 \times \text{LLOQ}$) and the associated 95% confidence intervals (CIs). The GMC will be calculated as the mean of the assay results after making the logarithm transformation and then back transformation to its original scale. Two (2)-sided 95% CIs will be constructed by back transformation of the CI for the mean of the logarithmically transformed assay results computed based on the Student's t distribution.

Exact 2-sided 95% CIs will be compiled using the Clopper-Pearson method for any proportions of subjects with *C difficile* toxin A– or toxin B–specific neutralizing antibody level \geq cutoff (LLOQ).

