9.3. Safety Analysis

The safety population will include all subjects who receive at least 1 dose of an investigational product. For the safety analysis, subjects will be analyzed according to the investigational product received. A descriptive summary will be presented for each vaccine lot, the combined vaccine lots, and the control group. For Tier 1 and Tier 2 events, the comparison between the pooled lots and control group will be performed.

Point estimates and the exact 2-sided 95% CIs will be compiled using the Clopper-Pearson method for proportions of subjects reporting each event.

The proportions of subjects reporting local reactions at the injection site (pain, erythema, and induration), and systemic events (fever, vomiting, headache, fatigue, new or worsening muscle pain, and new or worsening joint pain), on any day within the 7-day period after vaccination will be descriptively summarized by vaccine group and by each vaccination. Severities of local reactions and systemic events reported after each vaccination will also be descriptively summarized by vaccine group. Exact 2-sided 95% CIs will be presented with the proportions.

AEs and SAEs will be categorized according to Medical Dictionary for Regulatory Activities (MedDRA) terms. AEs will be summarized by vaccine group from signing of the ICD to 1 month after receipt of the third dose of investigational product. SAEs will be summarized by vaccine group from signing of the ICD to 1 month after receipt of the third dose of investigational product, and throughout the entire study. In general, all summaries will present the number and percentage of subjects experiencing at least 1 event and the number of events for each vaccine group, and the exact 2-sided 95% CIs.

The 3-tier approach will be used for the AE summary. Detailed analysis of each tier will be described in the SAP.

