### 3.5. Safety Endpoints

#### 3.5.1. Adverse Events

Safety endpoints will include Pfizer standard safety endpoints collected in the study. An adverse event (AE) is defined as any untoward medical occurrence and can therefore be any unfavorable and unintended sign (including an abnormal laboratory finding), symptom, or disease, whether or not related to the subject's participation in the study.

The time period for actively eliciting and collecting AEs for each subject begins from the time the subject provides informed consent through and including Visit 5 (Month 7). For subjects who are screen failures, the active collection period ends when screen failure status is determined.

Overall AEs by category (any AE, related AE, severe AE, serious AE, etc) will be summarized by the pooled lots and the control group from the date of the first dose to 1 month after receipt of the third dose of investigational product. AEs and SAEs will be summarized by the pooled lots and the control group from the date of the first dose to 1 month after receipt of the third dose of investigational product, by MedDRA term. SAEs will also be summarized by the pooled lots and the control group from the date of the first dose throughout the entire study by MedDRA term. In addition, a subject-level listing of all AEs reported will also be provided. In general, all summaries will present the number and percentage of subjects experiencing at least 1 event and the number of events for the pooled lots and the control group, and the exact 2-sided 95% confidence intervals (CIs).

The 3-tier approach will be used for the AE summary. Under this approach, AEs are classified into 1 of 3 tiers. Only for Tier 1 and Tier 2 AEs, the difference in the percentages between the *C difficile* vaccine (pooled lots) group and the placebo group, as well as the 2-sided 95% CI, will be provided. In addition, the p-value will be reported for Tier 1 events. CIs and p-values will be based on the Miettinen and Nurminen method.

**Tier 1 events:** These are prespecified events of clinical importance and, if any, are maintained in a list in the product's Safety Review Plan.

**Tier 2 events:** These are events that are not Tier 1 but are "common." A MedDRA preferred term (PT) is defined as a Tier 2 event if its incidence is  $\geq 1.0\%$  in at least 1 vaccine group (combined lots or placebo).

**Tier 3 events:** These are events that are neither Tier 1 nor Tier 2 events.

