### **3.5.3. Reactogenicity Data**

The reactogenicity data collected in the study e-diary will include local reactions (erythema/redness, induration/swelling, and pain at injection site) and systemic events (fever, vomiting, headache, fatigue, new or worsening muscle pain, and new or worsening joint pain). The e-diary will record reactogenicity data from Day 1 to Day 7 starting on the day of each vaccination.

All reactogenicity endpoints will be summarized as proportions of subjects with events, by vaccine group. Additionally, exact 2-sided 95% CIs for proportions will be provided as applicable.

A descriptive summary will be presented for each vaccine lot, the pooled lots, and the control group. For Tier 1 and Tier 2 events, comparison between the pooled lots and the control group will be performed.

Point estimates and the exact 2-sided 95% CIs (using the Clopper-Pearson method) will be provided for proportions of subjects reporting each event.

The proportion of subjects reporting local reactions at the injection site (pain, erythema, and induration), and systemic events (fever, vomiting, headache, fatigue, new or worsening muscle pain, and new or worsening joint pain), on any day within the 7-day period after vaccination will be descriptively summarized by vaccine lot, by pooled lots and control group, and by each vaccination. Severities of local reactions and systemic events reported after each vaccination will also be descriptively summarized by vaccine lot, pooled lots, and control group. Exact 2-sided 95% CIs will be presented with the proportions.

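### SAP 4.3 groups a mis-dosed subject's adverse events by the first dose or lot received without saying whether placebo counts; on the more natural reading, events after an erroneous active dose fall under placebo

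*SAP*

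**What the plan says.** SAP 4.3 has two rules for subjects who receive a dose or lot other than the one assigned. In the reactogenicity summaries they are kept up to the error, "at which point they will no longer be included". In the AE summaries, "such subjects will be included in the AE summary in the group according to the first vaccine dose/lot received". The AE rule has no cut-off, and I found no other place in either document that reassigns, censors or separately tabulates an AE starting after a later wrong dose.

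The protocol's principle, in section 9.3, is: "For the safety analysis, subjects will be analyzed according to the investigational product received". It does not say what happens when one subject receives two products. Protocol 8.4.4.1 foresees such errors, listing among its examples "The administration of an incorrect investigational product".

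SAP 3.5.1 summarises AEs for the pooled lots and the control group from the first dose to 1 month after the third. It plans a contrast for some events only: "Only for Tier 1 and Tier 2 AEs, the difference in the percentages between the" vaccine and placebo groups is given with a 95% CI. A preferred term that is not Tier 1 becomes Tier 2 when its incidence is at least 1.0% "in at least 1 vaccine group (combined lots or placebo"). The same section plans a subject-level listing of all reported AEs.

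**The concern.** Consider a subject who correctly receives placebo at Dose 1 and receives active vaccine by mistake at Dose 2 or 3. If placebo counts as the first dose, every AE in this subject through Month 7 is tabulated as placebo, including events that follow the active dose. That does not follow the protocol's principle of grouping by product received, and it moves a vaccine-exposed event into the smaller control arm. The reverse error, active first and placebo later, leaves the subject in the vaccine group, so only the error that places vaccine-exposed events under placebo is affected.

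At stake are the counts and percentages in the AE tables and, for Tier 1 and Tier 2 events, the planned difference and its interval. For a rarer Tier 3 event, including a Tier 3 SAE, only descriptive figures change. If the wording is left open, two programmers could also place the same subject in different columns.

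**Working it through.** **Which reading?**

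- *Placebo counts.* Protocol 9.2 refers to "vaccine group (active vaccine and placebo) as received", and the tier definition in SAP 3.5.1 also counts placebo as a vaccine group. The first dose received is then the first injection, whatever it contained.
- *Active vaccine only.* SAP 3.5.3 lists "each vaccine lot, the pooled lots, and the control group", so a lot is something apart from control. The randomisation (Lot 1, Lot 2, Lot 3, placebo) gives placebo no lot either. On this reading the subject is already grouped with vaccine.

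The first reading is the more natural one, but the text does not settle it.

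**Arm sizes.** Inputs from SAP 2.2.2: 263 evaluable per lot, 20% nonevaluable, 1:1:1:1. 263 / (1 − 0.20) = 328.75, rounded up to 329; 4 × 329 = 1316, the plan's own total. Placebo is therefore 329 and the pooled lots 3 × 329 = 987.

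**Size of one case.** 1/329 = 0.30 percentage points in placebo and 1/987 = 0.10 in the pooled lots, so the difference moves by about 0.40.

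**Illustrations.** Event counts are assumed. Differences are pooled lots minus placebo, with Miettinen-Nurminen 95% CIs. In each row one placebo-first subject has the event after active vaccine.

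| Assumed cases | First-dose rule, placebo counted | Any-active rule |
|---|---|---|
| 13 cases | 9/987 (0.91%) vs 4/329 (1.22%): −0.30 (−2.22 to 0.80) | 10/988 (1.01%) vs 3/328 (0.91%): +0.10 (−1.69 to 1.15) |
| 10 cases | 9/987 (0.91%) vs 1/329 (0.30%): Tier 3, no difference planned | 10/988 (1.01%) vs 0/328: Tier 2, +1.01 (−0.15 to 1.85) |
| 13 cases, none in other placebo subjects | 12/987 vs 1/329: +0.91 (−0.53 to 1.88) | 13/988 vs 0/328: +1.32 (0.15 to 2.24) |

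In the first row the sign changes but both intervals include zero. In the second, one case decides the tier. In the third, one case decides whether the interval excludes zero. The counts were chosen at or near these boundaries; they show what is possible, not what is expected.

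**How likely?** Assume m mis-dosed subjects and 10 cases of a term among the 987 + m vaccine-exposed subjects, all at equal risk. The chance that at least one case is in a mis-dosed subject is 1 − C(987,10)/C(987+m,10): 1.0% for m = 1, 3.0% for m = 3, 9.6% for m = 10.

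These are upper-end values, because they give a mis-dosed subject the risk of a full course. From the visit windows (28–42, 140–168 and 28–42 days), the share of follow-up after the active dose is:

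- Dose 3 error: 28/(42+168+28) = 11.8% to 42/(28+140+42) = 20.0%.
- Dose 2 error: (140+28)/(42+140+28) = 80.0% to (168+42)/(28+168+42) = 88.2%.

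If risk scales with that share f, the chance is about 1 − [987/(987 + f·m)]^10. For a Dose 3 error this gives 0.12–0.20% (m = 1), 0.36–0.61% (m = 3) and 1.2–2.0% (m = 10), about 5 to 8 times lower. A Dose 2 error stays close to the unscaled figures. The further coincidence of landing on a tier or interval boundary is not included.

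**The case against.** The best defence is that the harm depends on a disputed reading. The support for counting placebo comes from a neighbouring term, vaccine group, while SAP 4.3 speaks of a vaccine dose or lot. That stands, and it is why this is a gap in wording rather than a demonstrated misallocation.

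A reader might infer that SAP 4.3 contradicts Protocol 9.3. The documents do not support that. Protocol 9.3 is silent on mixed exposure, Protocol 9 leaves detailed methods to the SAP, and grouping by the first product actually received is one way to apply the principle.

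A reader might also infer that vaccine-related events would be hidden. They would not. SAP 3.5.1 lists every AE by subject, Protocol 5.6.3 records administration details on the CRF, and Protocol 8.4.4.1 has a medication error page. However, a listing does not correct a summary table, and the text specifies no flag for the product given at each dose.

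The contrast with reactogenicity is weaker than it looks. E-diary data are summarised per vaccination, so a subject can be dropped from a given dose onward. AE tables are cumulative, and dropping subjects there would lose SAEs. Any rule that keeps a subject in one group misplaces some events after a crossover, so the choice is partly a convention.

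Finally, such errors are likely to be rare. Cartons are assigned by the IRT system, and the vaccine and saline differ in appearance and are handled by unblinded staff. That stands too.

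**Conclusion.** A minor point, worth fixing because the fix is cheap. SAP 4.3 leaves open how a placebo-first subject given active vaccine in error is tabulated for AEs, and its more natural reading puts events after the active dose under placebo. Each such error followed by an event shifts about 0.30 points into placebo and 0.10 out of the pooled lots, assuming the planned arm sizes. An error with no event changes only the denominators. The number of mis-doses is not given, so the overall effect may be zero.

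It would be tempting to conclude that the vaccine-placebo safety comparison is biased. That goes too far: the tier and interval examples rest on assumed counts placed at or near boundaries, and the chances above are small.

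Lot-to-lot mix-ups do not alter the pooled AE tables. The primary lot-consistency analysis is unaffected, because SAP 4.1 requires all three doses of the randomised product. SAE reporting within 24 hours (Protocol 8.1) and data monitoring committee review (Protocol 9.5) do not depend on this rule.

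**What to change.** Before unblinding, make two changes:

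1. In SAP 4.3, state that for AE and SAE summaries any subject who received at least one dose of *C difficile* vaccine is counted in the pooled vaccine group. This settles the wording: it gives placebo-first subjects the result that the active-only reading already gives.
2. For mixed-exposure subjects, add to the AE listing planned in SAP 3.5.1 the product received at each dose and the onset of each event relative to each dose.

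The reactogenicity rule can stay as it is.

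The downside is that events before the erroneous active dose are then counted as vaccine events. By the visit windows, that placebo time is 12–20% of follow-up for a Dose 2 error and 80–88% for a Dose 3 error. This is the cautious direction for a safety table, and the listing makes it visible.

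The cost is a sentence or two, one programming rule and a few listing columns, all from data already collected.

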#### **4.4. Other Analysis Sets**

No other analysis set will be defined for the study.

### **5. GENERAL METHODOLOGY AND CONVENTIONS**

The primary objective of lot-to-lot consistency will be evaluated by GMC ratios, along with 95% CIs, for each *C difficile* toxin A– or toxin B–specific neutralizing antibody level determined at 1 month after Dose 3 using subjects in the EI population.

CCI

CCI

The *C difficile* toxin A- and toxin B-specific neutralizing antibody levels at each blood sampling time point will be summarized by GMCs and the associated 95% CIs. Any *C difficile* toxin A- or toxin B-specific neutralizing antibody level that is below the LLOQ will be assigned a value of  $0.5 \times \text{LLOQ}$ . GMCs and the associated 2-sided 95% CIs will be derived by calculating means and CIs on the natural log scale based on the t-distribution, and then exponentiating the results.

## 5.1. Hypotheses and Decision Rules

### 5.1.1. Analysis of the Primary Immunogenicity Endpoint

The primary objective of lot consistency will be tested for each *C difficile* toxin A- or toxin B-specific neutralizing antibody level determined at 1 month after Dose 3 using subjects in the EI population. The null hypothesis ( $H_0$ ) for the lot consistency is:

$$H_0 : | \ln(\mu_1) - \ln(\mu_2) | \geq \ln(2) \text{ OR } | \ln(\mu_1) - \ln(\mu_3) | \geq \ln(2) \text{ OR } | \ln(\mu_2) - \ln(\mu_3) | \geq \ln(2)$$

where  $\ln(\mu_1)$ ,  $\ln(\mu_2)$ , and  $\ln(\mu_3)$  are the means of the natural logarithm-transformed data of the *C difficile* toxin A- or toxin B-specific neutralizing antibody levels from subjects receiving *C difficile* vaccine from Lots 1, 2, and 3, respectively, measured 1 month after the third vaccination (Month 7) with *C difficile* vaccine. The neutralizing antibody-level data will be logarithmically transformed for analysis. GMC ratios, along with 2-sided 95% CIs, will be computed for each toxin A- or toxin B-specific neutralizing antibody concentration for each pair of lots (a total of 6 comparisons). The primary immunogenicity objective of the lot-to-lot consistency will be achieved if the 2-sided 95% CIs for the GMC ratios for all 6 comparisons are within the interval (0.5, 2), for both *C difficile* toxin A and toxin B.

CCI

CCI

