4.2. Exclusion Criteria

Subjects with any of the following characteristics/conditions will not be included in the study:

1. Investigator site staff members directly involved in the conduct of the study and their family members, site staff members otherwise supervised by the investigator, or subjects who are Pfizer employees, including their family members, directly involved in the conduct of the study.
2. Participation in other studies involving investigational drug(s)/vaccine(s) within 28 days prior to study entry through conclusion of the study.
3. Previous administration of an investigational *C difficile* vaccine or *C difficile* mAb therapy.
4. Proven or suspected prior episode of CDI.
5. Unstable chronic medical condition or disease requiring significant change in therapy or hospitalization for worsening disease within 8 weeks before receipt of investigational product.
6. Serious chronic medical disorders, including metastatic malignancy, severe chronic obstructive pulmonary disease (COPD) requiring supplemental oxygen, end-stage renal disease with or without dialysis, clinically unstable cardiac disease, or any other disorder that in the investigator's opinion precludes the subject from participating in the study.
7. Any bleeding disorder or anticoagulant therapy that would contraindicate intramuscular injection.
8. Any contraindication to vaccination or vaccine components, including previous anaphylactic reaction to any vaccine or vaccine-related components.
9. Subjects who may be unable to respond to vaccination due to:
 - Congenital or acquired immunodeficiency.
 - Receipt of systemic corticosteroids (≥ 20 mg/day of prednisone or equivalent) for ≥ 14 days within 28 days of enrollment.
 - Receipt of chronic systemic treatment with other known immunosuppressant medications, or radiotherapy, within 6 months of enrollment.

- Underlying bone marrow disorder such as myelodysplasia, myeloma, or myeloproliferative disorder, treated within the past year, or any history of bone marrow transplant.
- Malignancy that required treatment with chemotherapy (including the use of adjunctive and hormonal therapy), immunotherapy, radiation therapy, or antineoplastic target therapies within the past 24 months.

10. Receipt of blood products or immunoglobulins within 6 months before enrollment through conclusion of the study.

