7.2. Immunogenicity Assessments

Serum samples will be obtained for immunogenicity testing at Visit 1 (Month 0, immediately before Dose 1) and Visit 5 (Month 7, 1 month after Dose 3).

Both toxin A- and toxin B-specific neutralizing antibody levels will be measured. Approximately 20 mL (minimum of 10 mL and up to 20 mL) of blood will be collected to allow for adequate volume required for repeat testing or additional antigen-specific immunogenicity testing to be performed.

Refer to the SRM for details regarding serum sample management and storage.

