9.1. Sample Size Determination

In order to meet the immunogenicity primary objective, the study sample size estimate is based upon the evaluation of lot-to-lot consistency on the toxin A- and toxin B-specific neutralizing antibody in terms of GMCs, 1 month after the third vaccination (Month 7). A 2-fold equivalence margin is used for the study. Assuming the inherent difference for toxin A- and toxin B-specific neutralizing antibody responses is no more than 0.2 (in logarithmic scale) between any 2 lots, and the common standard deviations for toxin A- and toxin B-specific neutralizing antibodies are 0.899 and 1.485 (natural log value), respectively (based on the standard deviations for toxin A and toxin B at Month 7 in Study B5091009), a sample size of 263 evaluable subjects per lot will provide an overall 90% power to declare equivalence between all 6 comparisons for both toxin A and toxin B (see [Table 4](#)).

Table 4. Power Analysis (Primary Immunogenicity Endpoint)

Criteria	Neutralizing Antibody	Standard Deviation (Log Value)	Assume Observed Log GMC Difference	Number of Evaluable Subjects per Lot	Power ^a	Overall Power (3 Comparisons for Each Toxin)
95% CI for GMC ratio (any 2 lots) is between 0.5 and 2.0	Toxin A	0.899	0.2	263	>99.99%	>99.99%
	Toxin B	1.485	0.2	263	96.72%	90.47%
	Overall power (to meet equivalence for both toxin A and toxin B)					

a. Using a 2-fold equivalence margin for GMC ratios at a 2-sided, 0.05 alpha level.

Assuming a maximum nonevaluable rate of approximately 20%, a total of 1316 subjects need to be enrolled to meet the primary objective, with a randomization ratio of 1:1:1:1 (Lot 1: Lot 2: Lot 3: placebo).

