9.2.2. Analysis of the Primary Immunogenicity Endpoint

The primary objective of lot consistency will be tested at 1 month after Dose 3 for each *C difficile* toxin A- or toxin B-specific neutralizing antibody. The evaluable immunogenicity population will be used for lot-consistency hypothesis testing.

The null hypothesis (H_0) for the lot consistency is:

$$H_0 : |\ln(\mu_1) - \ln(\mu_2)| \geq \ln(2) \text{ OR } |\ln(\mu_1) - \ln(\mu_3)| \geq \ln(2) \text{ OR } |\ln(\mu_2) - \ln(\mu_3)| \geq \ln(2)$$

where $\ln(\mu_1)$, $\ln(\mu_2)$, and $\ln(\mu_3)$ are the means of the natural logarithm-transformed data of the *C difficile* toxin A- or toxin B-specific neutralizing antibody concentration from subjects receiving *C difficile* vaccine from Lots 1, 2, and 3, respectively, measured 1 month after the third vaccination (Month 7) with *C difficile* vaccine. The neutralizing antibody concentration data will be logarithmically transformed for analysis. GMC ratios, along with 95% CIs, will be computed for each toxin A- or toxin B-specific neutralizing antibody concentration for any 2 of the 3 lots (a total of 6 comparisons).

The primary immunogenicity objective of the lot-to-lot consistency will be achieved if the 2-sided 95% CIs on the GMC ratios for all 6 comparisons are within the interval (0.5, 2), for both toxin A and toxin B.

CCI

CCI

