### **2.2.2. Number of Subjects**

In order to meet the immunogenicity primary objective, the study sample size estimate is based upon the evaluation of lot-to-lot consistency on the toxin A- and toxin B-specific neutralizing antibody in terms of geometric mean concentrations (GMCs) 1 month after the third vaccination (Month 7). A 2-fold equivalence margin is used for the study. Assuming the inherent difference for toxin A- and toxin B-specific neutralizing antibody responses is no more than 0.2 (in logarithmic scale) between any 2 lots and the common standard deviations for toxin A- and toxin B-specific neutralizing antibodies are 0.899 and 1.485 (natural log value), respectively (based on the standard deviations for toxin A and toxin B at Month 7 in Study B5091009), a sample size of 263 evaluable subjects per lot will provide an overall 90% power to declare equivalence between all 6 comparisons for both toxin A and toxin B (see [Table 2](#)).

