### **6.1. Primary Endpoints**

#### **6.1.1. *C difficile* Toxin A– and Toxin B–Specific Neutralizing Antibody Levels**

**Endpoint:** *C difficile* toxin A–specific neutralizing antibody levels for each lot, expressed as GMCs

- Analysis time points: Visit 5 (1 month after the third vaccination)

- Analysis population: EI population
- Analysis methodology: GMC ratios and the 95% CIs
- Supporting objective: primary immunogenicity objective

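### The primary lot comparison leaves the pre-dose antibody level unused; adjusting for it would modestly tighten the toxin B intervals if baseline predicts Month 7

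*SAP*

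**What the plan says.** Protocol section 9.2.2 states the primary hypothesis on the lot means of log-transformed Month 7 levels: "GMC ratios, along with 95% CIs, will be computed for each toxin" and any two lots. SAP section 5.1.1 repeats this ("GMC ratios, along with 2-sided 95% CIs, will be computed for each toxin"), and SAP section 6.1.1 gives only "Analysis methodology: GMC ratios and the 95% CIs". SAP sections 5 and 5.2.2 describe t-based intervals on the log scale. No model or covariate appears in the readable primary text. All six intervals (three lot pairs, two toxins) must lie inside (0.5, 2).

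Both antibodies are also measured before vaccination. Protocol section 7.2 says "Serum samples will be obtained for immunogenicity testing at Visit 1 (Month 0, immediately before Dose 1) and Visit 5" (Month 7). In the readable text the Visit 1 values serve the GMCs by time point, the fold rises from baseline (Protocol Summary) and baseline serostatus (SAP section 3.4.3), but not the lot comparison.

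The sample size uses Month 7 standard deviations without reduction for baseline (Protocol section 9.1: "based on the standard deviations for toxin A and toxin B at Month 7 in Study B5091009"). It assumes the true lot difference "is no more than 0.2 (in logarithmic scale) between any 2 lots" (SAP section 2.2.2).

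**The concern.** Lots are randomized, so a linear model with the pre-dose level as a covariate estimates the same log GMC difference as the unadjusted comparison. If baseline predicts Month 7, its interval is narrower. If it does not, the cost is one degree of freedom out of 786.

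Precision matters here because success needs every interval inside the margin, and toxin B carries almost all the risk of failure: its planning SD is 1.485 natural-log units against 0.899 for toxin A. Less residual variance for toxin B therefore lowers the chance that truly consistent lots fail. The point concerns efficiency. The unadjusted interval already allows for chance imbalance at baseline and is not biased.

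**Working it through.** **Inputs from the documents.** Margin ln 2 = 0.693; two-sided 95% intervals; SD 0.899 (toxin A) and 1.485 (toxin B); log difference at most 0.2; 263 evaluable per lot; 20% nonevaluable; 1:1:1:1 allocation.

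**Assumption.** The documents do not give r, the correlation between log baseline and log Month 7 for the same toxin. I take 0 to 0.3 as the working range.

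**1. The plan's own figures.** For toxin B the standard error of a lot difference is 1.485 × √(2/263) = 0.1295. Per-pair power is about Φ((0.693 − 0.2)/0.1295 − t(0.975, 524)) = 96.74%. The noncentral t calculation gives 96.72%, as in the plan. Cubed for three pairs it is 90.48% (plan: 90.47%). Toxin A gives 99.9992% per pair and 99.998% cubed (plan: above 99.99%). Enrolment: 263/0.8 rounds up to 329, × 4 = 1316. The figures reproduce with the unadjusted SDs, so no baseline adjustment was assumed.

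**2. Joint power.** Three lots cannot all differ pairwise by 0.2, and the three comparisons are correlated, so cubing is conservative. I therefore computed joint power directly. Success means (largest − smallest lot mean) + t × s × √(2/263) < ln 2, with s pooled on 786 df (785 adjusted) and residual SD = 1.485 × √(1 − r²). The least favourable pattern with no pair more than 0.2 apart is 0, 0, 0.2.

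| r | Residual SD | Toxin B joint power | Equivalent n per lot, 263/(1 − r²) |
|---|---|---|---|
| unadjusted | 1.485 | 94.11% | 263 |
| 0 | 1.485 | 94.11% | 263 |
| 0.1 | 1.478 | 94.35% | 265.7 |
| 0.2 | 1.455 | 95.04% | 274.0 |
| 0.3 | 1.417 | 96.09% | 289.0 |

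At r = 0.5 power would be 98.6%, but nothing in the documents supports that value. A 2,000,000-draw simulation agrees within 0.03 points. Subject-level simulation of the model (40,000 trials per setting) gave 94.0% unadjusted and 93.9% adjusted at r = 0, and 94.2% and 96.1% at r = 0.3. Toxin A at the same pattern is 99.9985% unadjusted.

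**3. Closer lots.** Unadjusted to adjusted at r = 0.3:
- 0, 0.1, 0.2: 96.1% to 97.5%
- 0, 0, 0.15: 97.6% to 98.6%
- 0, 0, 0.1: 99.1% to 99.5%
- identical lots: 99.8% to 99.9%

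**4. Interval width at r = 0.3.** The half-width falls from 1.963 × 1.485 × √(2/263) = 0.2542 to 0.2425 log units. The largest observed ratio that still passes moves from exp(0.6931 − 0.2542) = 1.55 to exp(0.6931 − 0.2425) = 1.57.

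**5. Values below the LLOQ and missing baselines.** Prior disease is excluded ("Proven or suspected prior episode of CDI", Protocol section 4.2), and any "neutralizing antibody level that is below the LLOQ will be assigned a value of" half the LLOQ (SAP section 5), so many baselines may share one value. With latent r = 0.3, an assumed baseline log SD of 1, and 50%, 80% or 95% of baselines below the LLOQ, the gain at 0, 0, 0.2 is 1.7, 1.1 or 0.4 points. With 5% of baselines also missing and set to a common mean, it is 1.5, 1.0 or 0.4 points.

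**6. Type I error.** With lot means 0, ln 2/2, ln 2 and 5% missing baselines, simulated rejection, adjusted and unadjusted, was 2.4% and 2.4% at r = 0, 2.3% and 2.3% at r = 0.3, and 2.6% and 2.5% at r = 0.5. The nominal level is 2.5%, and adjustment shows no material inflation.

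**The case against.** The strongest reply is that nothing is broken. Unadjusted log means are a legitimate choice for randomized lots, stated consistently in both documents and matched by the sample size. The benefit is conditional on an r that the documents do not give. At r = 0 nothing is gained, and the exclusions and the LLOQ rule point to a low value. The 0, 0, 0.2 pattern and 263 evaluable per lot are the plan's worst case: with 10% nonevaluable (assumed; 329 × 0.9 ≈ 296 per lot), power at that pattern is 96.5% unadjusted and 97.8% at r = 0.3. Against this stand an amendment, ethics approval and a changed primary estimator in a SAP already at Version 3. An adjusted ratio would also no longer equal the ratio of the reported lot GMCs, and the test would need a rule for missing baselines. Redacted text next to the primary analysis may hold an adjusted supportive analysis.

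Most of this stands, and it limits the point to a modest, conditional gain. It does not remove it. The readable primary rule ignores a covariate that the trial already collects, and using it costs essentially nothing in power if r is zero. The unadjusted ratios can still be reported beside the adjusted ones. A supportive analysis in redacted text would not change the primary rule. The gain is also larger if planning assumptions slip: at an assumed 230 evaluable per lot, joint power at 0, 0, 0.2 rises from 90.3% to 93.1% at r = 0.3.

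**Conclusion.** The point holds as an efficiency recommendation. The primary test is valid, unbiased and powered as stated. Under the plan's least favourable pattern with 263 per lot, same-toxin baseline adjustment raises toxin B joint power by 0 to 2.0 points for r from 0 to 0.3 (94.1% to at most 96.1%). At r = 0.3 the risk of failing falls from 5.9% to 3.9%. The gain shrinks towards zero as lots become more alike or as more baselines fall below the LLOQ. Toxin A power does not change in practice. The size rests on an assumed r. The conclusion covers only the readable primary analysis and says nothing about supportive analyses that may be redacted.

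**What to change.** If the trial is still blinded, obtain the three lot-pair ratios for each toxin from one linear model of ln(Month 7 level), fitted to the three vaccine lots in the evaluable immunogenicity population. Use two fixed terms:
- lot;
- ln(baseline level of the same toxin), with values below the LLOQ set to half the LLOQ as the SAP already does.

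Set a missing baseline to the mean ln(baseline) over the three lots combined, one value for all lots. The population definition in SAP section 4.1 does not list a baseline result as a criterion, so this keeps every evaluable subject. Apply the unchanged (0.5, 2) rule to the exponentiated adjusted 95% intervals, and report the unadjusted ratios as supporting.

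The cost is one degree of freedom, one model statement in SAP sections 5.1.1 and 6.1.1, and a matching change to Protocol section 9.2.2. Protocol section 9 and SAP section 2 require a protocol amendment for a major change of this kind, with IRB/EC approval, and it should be complete before unblinding. No new samples, data or subjects are needed. The planning SDs come from Study B5091009. If that study also holds baseline levels, which the documents do not say, estimate r there first and amend only if it is not negligible. If the data are already unblinded, leave the primary analysis as it is.
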